6.2 CHOICE OF COMPARATOR OR CONTROL

The present study is designed to find the maximum tolerated dose (MTD) of the combination of NOX66 with doxorubicin in patients with STS, and therefore no control group or comparator is needed for this study.

All patients will be treated with doxorubicin which is widely held as the initial standard of care for metastatic STS. One week prior to initiation of doxorubicin, patients in the Dose-Escalation Cohorts will also receive 7 days of NOX66 monotherapy which has been shown to be cytotoxic to sarcoma cell lines (n=19) *in vitro* with IC₅₀ values ranging from 0.3 to 18.4 μ M (median 5.2 μ M).

In the Dose Expansion Cohort, all patients will be treated for 1 day with NOX66 (at the MTD of the combination of NOX66 and doxorubicin), before receiving doxorubicin on Day 2 of a 21-day cycle. On Days 2 to 7, NOX66 will be given at the same dose as on Day 1. No therapy is administered from Days 8 to 21 of each treatment cycle.

All patients are eligible to receive up to 6 cycles of doxorubicin.

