8.3.3 DEFINITION OF DLT

Any of the following, if judged to be associated with the combination of NOX66 and doxorubicin (i.e., possibly-, probably-, or definitely related), during Cycle 1, at each dose level, will be considered a DLT using the NCI-CTCAE Version 5.0:

- 1) Grade 3 non-hematological toxicities (excluding alopecia) with the following exceptions:
 - i. Grade 3 nausea/vomiting or diarrhea <72 hours with adequate antiemetic and other supportive care
 - ii. Grade 3 fatigue <1 week
 - iii. Grade 3 electrolyte abnormality that lasts 24 to 72 hours (Investigator's discretion for timeframe), is not clinically complicated and resolves spontaneously or responds to conventional medical interventions.
- 2) Grade 4 non-hematologic (non-laboratory) toxicity of any duration
- 3) Grade 3 or Grade 4 febrile neutropenia of any duration not caused by doxorubicin. *It is well known that a dose-dependent, reversible leukopenia and/or neutropenia are the predominant manifestations of doxorubicin hematologic toxicity and are the most common acute dose-limiting toxicities of this drug. With the recommended dose schedule, leukopenia is usually transient, reaching its nadir 10 to 14 days after treatment with recovery usually occurring by the 21st day.*
- 4) Grade 3 thrombocytopenia in combination with a Grade 3 or greater blood and lymphatic system disorder, not attributable to doxorubicin
- 5) Grade 3 AST or ALT that is associated with a Grade 2 or greater rise in bilirubin

Based on the limited experience with NOX66 and the known toxicities of doxorubicin, it is possible that there may be overlapping toxicities in terms of anemia, neutropenia, nausea, and asthenia.

If patients develop any DLT during NOX66 monotherapy and/or during Cycles 2 to 6 of the combination, these will be considered "DLT equivalent toxicity" and will be recorded in the eCRF. Growth factor support (except during Cycle 1 in the Dose Escalation Cohorts) or other supportive medication (anti-emetics) at any cycle may be given at the discretion of the Investigator.

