14.3.4 ADVERSE EVENTS

An AE will be deemed treatment emergent (TEAE) if it starts or worsens in severity or toxicity after the beginning of treatment, whether with idronoxil or with idronoxil + doxorubicin.

Adverse events will be coded using the MedDRA Dictionary, Version 22.0 (or higher). Treatment emergent adverse events will be summarized by MedDRA Preferred Term and System Organ Classification for each dose group. Separate summaries will be provided for TEAEs with onset prior to the first dose of doxorubicin, with onset during the first cycle of idronoxil+ doxorubicin therapy, and for TEAEs with onset after the end of the first treatment cycle.

The toxicity of an AE will be assessed by the NCI-CTCAE, Version 5.0. Summaries of TEAEs will be provided by dose group and toxicity grade. Summaries of TEAEs will also be provided by dose group and Investigator-reported severity and by dose group and Investigator-reported relationship to study treatment.

A summary will be provided of the overall incidence and the incidence of component terms for the Standardized MedDRA Queries (SMQs) for Cardiac Failure and for Cardiomyopathy.

A separate summary will be provided of Serious Adverse Events (SAEs) by dose group. Summaries will be presented for all SAEs, for treatment-emergent SAEs, for treatment-emergent SAEs that occur prior to the first dose of doxorubicin, during the first cycle of idronoxil + doxorubicin combination treatment, and after the end of the first cycle of combination treatment.

Deaths on study or within 30 days after a patient exits the study will be summarized by treatment. A listing of all deaths will be provided.

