15.2.1.1 AE Reporting

All AEs are graded according to NCI-CTCAE v5.0. AEs are captured from the time of consent and must be reported in the eCRF.

. Some events may make the patient ineligible for enrollment. Unanticipated events should be reported to the IRB, according to its requirements. Patients will be questioned at every visit after the first dose until the last follow-up visit regarding the occurrence and nature of any TEAEs. All TEAEs will be reported, whether or not they are deemed to be related to investigational product.

A description of the event or diagnosis including dates, severity, relationship to the investigational product, action taken and outcome, and whether or not the event was also serious, must be reported on the AE eCRF for each TEAE recorded in the patient's chart.

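### TEAEs are sorted into treatment periods by onset alone, although worsening also makes a TEAE, and the first two periods overlap on Cycle 1 Day 1

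*Combined protocol and SAP*

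**What the plan says.** Section 14.3.4 defines the event set broadly: "An AE will be deemed treatment emergent (TEAE) if it starts or worsens in severity or toxicity after the beginning of treatment". It then gives three summaries by preferred term and system organ class, all keyed to onset: "Separate summaries will be provided for TEAEs with onset prior to the first dose of doxorubicin, with onset during the first cycle" of combination therapy, and "for TEAEs with onset after the end of the first treatment cycle". No sentence says which period a worsening belongs to.

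The same section plans TEAE summaries by toxicity grade, severity and relationship within dose group. None of these is stated to be split by period. Treatment-emergent SAEs are split by when they happen, without reference to onset: "treatment-emergent SAEs that occur prior to the first dose of doxorubicin, during the first cycle of idronoxil + doxorubicin combination treatment", and after that cycle.

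Section 15.2.1.1 sets what is recorded for each event: "A description of the event or diagnosis including dates, severity, relationship to the investigational product", plus action and outcome. It captures events from consent onward. Neither it nor Section 16 says whether a grade change updates the existing record or opens a new one.

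On timing, Section 8.1.1 gives the escalation cohorts a NOX66 lead-in and a washout before Cycle 1, with doxorubicin on Day 2 of each cycle. The expansion cohort has no lead-in; before doxorubicin, "all patients will be treated for 1 day with NOX66" (Section 6.2).

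**The concern.** The definition and the sorting rule do not match. Worsening can bring an event into the TEAE set, but only its first appearance decides which table it enters. An event that is mild on NOX66 alone and worsens once doxorubicin is added is just what the lead-in design should make visible. Under the stated rule it may never reach a combination table.

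The second primary objective (Section 7.1) is the safety and tolerability of NOX66 alone and with doxorubicin, and the synopsis promises AE summaries on that split. The period tables are the stated AE tables that make it. The protocol also expects the situation to arise: "it is possible that there may be overlapping toxicities in terms of anemia, neutropenia, nausea, and asthenia" (Section 8.3.3).

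The second problem is a boundary. Doxorubicin starts a day after the cycle does, so the first two periods, as worded, share that day.

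**Working it through.** The plan states no figure here, so the check sets the rules side by side and applies them to example events.

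**Step 1: timeline.** Inputs are Sections 8.1.1 and 6.2 and Table 4, footnote 12.
- Escalation: 7 days of monotherapy + 5 days of washout + Cycle 1 Day 1 = 13 days from first NOX66 to doxorubicin. The first 7 + 5 = 12 days lie outside Cycle 1; the last day lies inside it.
- Expansion: 1 day, wholly inside Cycle 1.
- These lengths are nominal. Section 11.6.2 allows one day either side for the Day 2 visit.

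**Step 2: apply the onset rule.** The documents leave the recording convention open, so both possibilities are shown.

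| Event | One evolving record | New record at each grade increase |
|---|---|---|
| A. Starts in the lead-in, worsens in Cycle 1 after doxorubicin | Pre-doxorubicin only | Pre-doxorubicin and Cycle 1 |
| B. Starts in screening, worsens in Cycle 1 after doxorubicin | Pre-doxorubicin only | Cycle 1 |
| C. Starts on Cycle 1 Day 1, after NOX66 and before doxorubicin | Pre-doxorubicin and Cycle 1 | Pre-doxorubicin and Cycle 1 |

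**Step 3: read the table.**
- In A and B the combination summary loses the event under one record per event and keeps it under new records.
- B is the odder case. The event is treatment-emergent only because it worsened after doxorubicin, yet its onset places it before doxorubicin.
- C is counted twice under either convention.
- A can occur only in the escalation part. B can occur in both parts. In the expansion cohort, C covers every TEAE that starts between the first NOX66 dose and the first doxorubicin dose.

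**Step 4: related rule.** Section 14.3.1 places an event with no start date at all one minute after the first idronoxil dose. In escalation that is the pre-doxorubicin period; in expansion it is the shared day.

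**Step 5: size.** The number of events moved depends on how many worsen after doxorubicin and what share of those began before it. The documents give neither figure, so no percentage is offered.

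**The case against.** The strongest reply is that Section 16.1.1 counts a worsening of a sign or symptom as an adverse event in its own right. A grade increase after doxorubicin would then have its own onset and enter the right table. This reading is open, and it is why the point is conditional for cases A and B. Other text leans the other way. Section 16.1.1 describes aggravation relative to the baseline condition, and Section 14.3.1 fixes baseline for measurements before first study drug with no reset at Cycle 1. Table 6 has no outcome that closes a record because the event worsened. Section 16.2.1 treats a non-serious event that becomes serious as follow-up. None of this settles the matter, and about 12 sites could record such events differently.

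Second, other outputs limit the harm, and this stands:
- DLTs are judged directly at the end of Cycle 1 (Section 8.3.4), so dose escalation and the MTD do not rest on these tables.
- DLT-equivalent toxicity in monotherapy and in Cycles 2 to 6 is recorded separately (Section 8.3.3).
- Laboratory CTC grades are summarized at each scheduled collection (Section 14.3.5), including Days 9 and 16 of each cycle (Section 11.4.2.4). That partly covers anemia and neutropenia, but not nausea or asthenia.
- Relationship has its own summary, and a table by onset does not itself assign cause.

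Third, Section 14.3.12 leaves presentation and data-handling detail to a separate SAP that is not supplied. It could settle how grade changes are recorded. It does not remove an onset rule and overlapping boundaries that the protocol already states.

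**Conclusion.** The point holds as a wording defect in a stated rule that bears on a primary objective. The overlap on Cycle 1 Day 1 follows from the text alone. The loss of worsened events from the combination summaries follows from the literal rule, on the assumption of one evolving record per event.

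A reader might infer three stronger things that the documents do not support:
- **That Grade 3 toxicity will be displayed under NOX66 alone.** The period summaries are by term and organ class, and the grade summaries have no stated period split. What follows is a misplaced count, not a misplaced grade.
- **That the bias can be put as a percentage.** That would need two rates the documents do not contain.
- **That every pre-doxorubicin TEAE in the expansion cohort is counted twice.** An event that began in screening and worsened on treatment has its onset before Cycle 1, so it falls only in the first summary.

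The size of the effect is unknown. The change is worth making because it is cheap and the affected tables describe what the lead-in was designed to show.

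**What to change.** In Section 14.3.4:
1. Count a TEAE in each period in which it starts or increases in grade, and show the maximum grade reached within that period. Support this with dated grade changes, or with a new AE record at each increase, and put the chosen convention in the eCRF completion instructions.
2. Make the periods disjoint: first NOX66 dose to just before the first doxorubicin dose; first doxorubicin dose to the end of Cycle 1; after Cycle 1.
3. Use the same rule and boundaries for treatment-emergent SAEs, so that the two sets of tables can be read together.

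The cost is protocol and SAP wording, an eCRF instruction and table programming, with no added visits or patients. One small downside is that a patient may appear in more than one period table for the same term, so the tables need a footnote saying that counts do not add across periods.

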14.3.5 LABORATORY SUMMARIES

Safety laboratory results will be summarized by dose group. At each scheduled laboratory collection, the laboratory result and the change from baseline in laboratory result will be summarized for each laboratory parameter. CTC grades will be assigned to laboratory results where they are defined, and the frequency and percentage of each CTC grade will be included in the summary.

Shift tables will be provided for change in CTC grade from baseline to end of study and from baseline to worst grade on study.

Brain type natriuretic peptide measurements will be summarized using descriptive statistics at baseline and at Cycles 1, 3, 5, and the end of Cycle 6 or Early Termination (if occurs prior to the end of Cycle 6). The number and percentage of patients with BNP laboratory values greater than 500 pg/mL and with BNP laboratory values between 100 and 500 pg/mL will be presented.

Blood levels of chemokines and cytokines will be summarized using descriptive statistics at baseline, Day 7 of Monotherapy period (only for Dose Escalation), at Cycle 3, and at the end of Cycle 6 or at Early Termination (if occurs prior to the end of Cycle 6).

Listings of genetic mutations at baseline and at end of Cycle 6 or Early Termination will be made.

Blood levels of ENOX2 will be summarized using descriptive statistics at baseline, at Cycle 3, and at the end of Cycle 6 or at Early Termination (if occurs prior to the end of Cycle 6). These levels will also be assessed in the same manner for patients in the Dose Escalation Cohorts, including those on Day 7 of Monotherapy period, if the samples are collected.

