	
and resolves spontaneously or responds to conventional medical interventions.
 
2) Grade 4 non-hematologic (non-laboratory) toxicity of any duration
 
3) Grade 3 or Grade 4 febrile neutropenia of any duration not caused by doxorubicin. It is well known that a dose-dependent, reversible leukopenia and/or neutropenia are the predominant manifestations of doxorubicin hematologic toxicity and are the most common acute dose-limiting toxicities of this drug. With the recommended dose schedule, leukopenia is usually transient, reaching its nadir 10 to 14 days after treatment with recovery usually occurring by the 21st day.
 
4) Grade 3 thrombocytopenia in combination with a Grade 3 or greater blood and lymphatic system disorder, not attributable to doxorubicin
 
5) Grade 3 AST or ALT that is associated with a Grade 2 or greater rise in bilirubin
 
Growth factor support can be administered during combination cycles, except during Cycle 1 in the Dose Escalation Cohorts. The recommended Phase 2 dose (RP2D) may be defined as the highest dose administered at which no more than 1 patient (out of 6) experiences a DLT and the dosage form, including the dosing frequency, is acceptable to patients.
 
Cohort Expansion
 
After the Dose Escalation Part is completed, 16 patients will be enrolled into a Dose Expansion Cohort at the MTD of the combination of NOX66 and doxorubicin. All patients will enter directly into 21-day combination cycles and will be given NOX66 therapy for 7 days and doxorubicin will be administered on Day 2 (1 hour after the morning dose of NOX66 dose is administered). This will be followed by a 2-week rest period. Treatments will continue up to 6 cycles.
 
Treatment will be terminated upon disease progression, unacceptable toxicity or a maximum of 6 cycles. In patients who develop Grade 3 or 4 toxicity determined to be related to NOX66, the Investigator may reduce the dose or frequency of dosing by one level so that the patients can remain in the study. All patients will be actively followed up for about 14 months following completion of Cycle 6 (including scheduled visits every 3 months) followed by telephone follow-up / chart review, for progression free survival (PFS) and overall survival (OS), at 15 and 18 months following completion of Cycle 6.
 
Pharmacokinetics
 
During the Monotherapy phase, on Day 1 blood samples will be collected for PK analysis of idronoxil at pre-dose (within 15 minutes prior to dosing) and at 1, 2, 3, 4, 6, and 8 hours post application. On Day 2, a pre-dose sample will be collected prior to application of NOX66. This sample can be collected in the clinic or at the patient's home. Exact times for dosing and blood sampling will be recorded. If a bowel movement occurs, during the collection period, the time of each bowel movement should be recorded, and the collections should continue as planned. Blood plasma will be analysed for the quantification of

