	
replaced in the Monotherapy period, in Cycle 1 or 2, the number of patients will be higher than 34.
 
Analysis sets:
 
There will be two analysis sets
 
• Safety Set: All patients treated with at least one dose of idronoxil will be included in the Safety Set (SS). All analyses of safety, toxicity, and PK will be performed for this set.• Full Analysis Set (FAS): All patients who completed at least one cycle of combination therapy (at any NOX66 dose). 
Analyses of efficacy, tolerability, and biomarkers will be performed for the FAS. Separate summaries may be provided for patients participating in the Dose Escalation and Dose Expansion parts.
 
Safety (Primary analysis):
 
The safety profile will be based on Serious Adverse Events (SAEs), Treatment Emergent Adverse Events (TEAEs), standard clinical laboratory parameters (clinical chemistry, hematology, urinalysis), vital signs measurements, ECG parameters, and physical examination findings.
 
Adverse events (AE) will be coded using the Medical Dictionary for Regulatory Activities and summarized by dose when NOX66 is given alone or in combination with doxorubicin. The number and percentage of patients reporting TEAEs will be calculated overall, by system organ class, and by preferred term for each dose level. Adverse events will also be graded for severity according to the National Cancer Institute Common Terminology Criteria for Adverse Events, Version 5.0.
 
Serious Adverse Events (SAEs) will be summarized separately.
 
Cardiac AEs (including clinically significant abnormalities in ECG rhythm and waveform morphology reported as TEAEs) and changes in echocardiographic parameters will be summarized.
 
Descriptive statistics will be provided for demographics, baseline characteristics, and exposure to treatment by cohort.
 
Univariate summary statistics will be provided by dose group at each visit for quantitative laboratory parameters and vital signs and for the change from baseline in these parameters. For laboratory values and vital signs with defined CTC grades, shift tables will be provided for CTC grades from baseline to end of study and from baseline to worst value on study.
 
Univariate summary statistics will be presented for ECG parameters for the value at each measurement time point and the change from baseline to each measurement time point. A similar analysis will be provided for the worst value of each ECG parameter on study.
 
Findings from physical examinations and ECOG performance status will be summarized by dose of NOX66 given alone or in combination with doxorubicin.
 
Pharmacokinetics (Secondary analysis):
 
Individual blood concentration-time data and blood PK parameters will be summarized using descriptive statistics by dose and sampling time for idronoxil and metabolites. Separate summaries will be provided for PK

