10.1.4 DOXORUBICIN, GROWTH FACTORS, DEXRAZOXANE

For details on doxorubicin see Section 8.2. The use of growth factors and dexrazoxane is permitted to reduce myelosuppression and cardiac toxicity due to doxorubicin. Growth factors may be used to treat neutropenia and thrombocytopenia in all cycles in the Dose Escalation and Expansion Cohorts (except for Cycle 1 in the Dose Escalation Cohorts). The degree of myelosuppression may be increased at Cycles 5 and 6 with the use of dexrazoxane. Doxorubicin should be given within 30 minutes after beginning the infusion with dexrazoxane. [Note: For breast cancer patients, dexrazoxane is recommended when doxorubicin cumulative dosage is $\geq 300 \text{ mg/m}^2$].

These products will be obtained as standard of care and are prescribed based on the Investigator's clinical judgement.

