11.1.2.4 Exploratory Analysis

Factors which may contribute to the overall response to the combination of NOX66 and doxorubicin will be evaluated and include.

- NOX66 dose or exposure
- Doxorubicin exposure
- Histopathology
- Cytokine and chemokine response
- ENOX2 response
- Specific genetic mutations
- Lipidomic profiling (capturing over 300 lipid species as determined by liquid chromatography-tandem mass spectrometry)
- Suppository Acceptance Questionnaire

For the safety and efficacy parameters, these are the standard measures used to assess the effects of a novel chemotherapeutic agent alone and in combination with a cytotoxic agent like doxorubicin. The safety profile of doxorubicin is well known and greater myelosuppression, or unexpectedly elevated levels of AST, ALT, and bilirubin than what one would expect with this agent given alone is suggestive of an additive effect from NOX66. The assessments of cardiac function with echocardiograms and biomarkers BNP and troponin 1 are well established to detect potential doxorubicin induced cardiac toxicity.

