14.3 STATISTICAL METHODOLOGY

14.3.1 GENERAL STATISTICS METHODS

All data will be summarized by idronoxil dose group. For safety analyses, a summary group consisting of all dose groups combined may also be presented.

For all measurements, the baseline value will be the last measurement taken before the first dose of study drug, whether idronoxil or of idronoxil + doxorubicin depending on the cohort.

Standard summary statistics will be presented for all measurements. For continuous variables, the standard summary statistics will be the number of observations (n), mean, standard deviation, median, minimum and maximum. For categorical variables, the standard summary statistics will be the number and percentage of observations in each category. Categories that are specified on the eCRF which contain no observations will be presented in the data summaries with a value of 0.

An AE with a completely missing start date will be assumed to start one minute after the date-time of the first idronoxil dose. If the severity of a reported AE is missing, it will be assumed that the event is severe; similarly, if the relationship of a reported AE to study treatment is missing, it will be assumed that the event is definitely related to treatment. No other missing data will be imputed. Incomplete start dates for Adverse Events and Concomitant Medications and incomplete end dates for AEs will have missing parts imputed by a conservative procedure which will be specified in the Statistical Analysis Plan (SAP).

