14.3.3 EXPOSURE TO TREATMENT

The summary of exposure will include the final idronoxil and doxorubicin doses, and the cumulative doses of idronoxil and doxorubicin received over the course of the entire study. Summaries will also be provided of the number of idronoxil treatments missed, the number of changes in the idronoxil and doxorubicin doses, the number of patients receiving dexamethasone, and the dexamethasone dose.

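### Cycle 1 and worst-grade myelosuppression at the MTD may be understated relative to other doses, because dose-group tables mix patients barred from growth factors in Cycle 1 with patients allowed them

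*Combined protocol and SAP*

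**What the plan says.** The growth-factor rule appears in the synopsis, in 8.3.3, in 10.1.4 and in 10.4, and the four agree. The synopsis reads: "Growth factor support can be administered during combination cycles, except during Cycle 1 in the Dose Escalation Cohorts". Section 10.1.4 gives the purpose: "Growth factors may be used to treat neutropenia and thrombocytopenia in all cycles in the Dose Escalation and Expansion Cohorts", with the same exception for escalation Cycle 1. Use is permitted, not required; 8.3.3 and 10.1.4 leave it to the Investigator.

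The grouping rule is in Section 14. Section 14.3.1 sets it generally: "All data will be summarized by idronoxil dose group". Section 14.3.5 repeats it for laboratory data: "Safety laboratory results will be summarized by dose group". Section 14.3.4 also tabulates TEAEs by dose group, with a separate summary for onset in the first combination cycle but none by study part. The only mention of a split by part is in the synopsis: "Separate summaries may be provided for patients participating in the Dose Escalation and Dose Expansion parts". Section 14 does not take it up.

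The exposure summary in 14.3.3 covers doses received, treatments missed and "the number of changes in the idronoxil and doxorubicin doses". The one supportive drug it names is dexamethasone; growth factors are not listed. Section 10.4 does record all concomitant medication on the eCRF.

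On interpretation, 11.1.2.4 reads: "greater myelosuppression, or unexpectedly elevated levels of AST, ALT, and bilirubin than what one would expect with this agent given alone is suggestive". The thing suggested there is toxicity added by NOX66.

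**The concern.** Permission to use growth factors in Cycle 1 is tied to study part, and study part is tied to dose, because every expansion patient is treated at the MTD. A reader comparing dose columns in a Cycle 1 haematology table would be comparing doses and support rules together. Without a table of growth-factor use, the reader could not tell how far the rules mattered in practice.

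What is at stake is the description of marrow toxicity at the dose carried forward. Safety is a primary objective, and the plan treats excess myelosuppression as a sign of added toxicity from NOX66. If support raises counts in the 16 expansion patients, the MTD column looks milder than it would under the rule that governs the other columns, and a real dose trend could be flattened.

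**Working it through.** **Who is in the MTD column.** The planned totals can be rebuilt. The maximum is 3 dose levels × 6 + 16 = 34, and the minimum is 3 + 3 + 6 + 16 = 28; both match the synopsis. The MTD is defined on 6 escalation patients (8.3.1; 8.1.1 for the 1800 mg level), and 16 expansion patients follow at that dose (8.1.2). The column therefore holds 6 + 16 = 22 patients, of whom 16/22 = 73% come from expansion.

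**Which tables are affected.** The rules differ only in Cycle 1. That reaches the Cycle 1 laboratory visits, the first-cycle TEAE table, and the tables that take Cycle 1 in with later cycles, including the shift to worst grade on study. From Cycle 2 the same rule applies in both parts.

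**Expected size.** Let p be the Cycle 1 Grade 3-4 neutropenia rate without support, u the share of expansion patients given growth factor in Cycle 1, and RR the relative risk with growth factor. None of these is in the documents; all values below are assumptions.

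Expansion rate = p × [1 − u(1 − RR)]

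Pooled MTD rate = {6p + 16p[1 − u(1 − RR)]}/22 = p × [1 − (16/22) × u × (1 − RR)]

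With p = 50%:

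| Uptake u | RR | Expansion rate | Pooled MTD rate |
|---|---|---|---|
| 0 | any | 50% | 50% |
| 25% | 0.6 | 45% | (3 + 7.2)/22 = 46.4% |
| 50% | 0.6 | 40% | (3 + 6.4)/22 = 42.7% |
| 100% | 0.7 | 35% | (3 + 5.6)/22 = 39.1% |
| 100% | 0.6 | 30% | (3 + 4.8)/22 = 35.5% |
| 100% | 0.5 | 25% | (3 + 4.0)/22 = 31.8% |
| 100% | 0.3 | 15% | (3 + 2.4)/22 = 24.5% |

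In every row the 6 escalation patients at the MTD keep an expected rate of 50%, so the distortion comes wholly from pooling.

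**Can the dose order reverse?** Take true unsupported rates of 40% at a lower dose (6 patients) and 50% at the MTD. The expected pooled MTD rate stays above 40% at half uptake with RR 0.6 (42.7%). It falls below at full uptake with RR 0.6 (35.5%) or RR 0.4 ((3 + 3.2)/22 = 28.2%). The exact binomial chance that the observed pooled MTD rate is strictly below the lower-dose rate is:

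- no growth factor: 31%
- half uptake, RR 0.6: 43%
- full uptake, RR 0.6: 57%
- full uptake, RR 0.4: 70%

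With only the 6 escalation patients at the MTD the chance is 26% whatever the uptake. It is not directly comparable with the 31%, because ties are more common between two groups of 6.

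**The case against.** Several points on the other side have force.

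- **Permission is not use.** Growth factors are discretionary, and with no uptake there is no bias. A reader might infer that neutropenia at the MTD is certain to be understated; the documents support only that it may be.
- **Use is described mainly as treatment.** Support given after a low count does not erase a Grade 3-4 value already recorded. This weakens the full-uptake rows, which amount to universal prophylaxis that no section describes. It does not remove the concern. Section 10.1.4 also allows use to reduce myelosuppression. The stated leukopenia nadir, 10 to 14 days after doxorubicin given on Day 2, falls on cycle Days 12 to 16, while counts are taken on Days 9 and 16 (11.4.2.4). Support started after a low Day 9 count could raise the Day 16 value in expansion but could not be given in escalation.
- **The split may be made anyway.** The synopsis allows it, and 14.3.12 leaves presentation to an SAP approved before expansion opens. But it is optional, follows directly on the sentence about Full Analysis Set analyses, and is not carried into the safety sections.
- **Dose selection is untouched.** This stands in full. A reader might infer that the MTD is compromised. MTD and DLT decisions rest on escalation patients in Cycle 1, where support is barred, and the RP2D is defined by DLTs and acceptability of the dosage form.
- **Section 11.1.2.4 compares with doxorubicin alone.** It does not set up a comparison across NOX66 doses, so a flattened dose trend is not the failure of a pre-stated marker. A lowered pooled rate would still weaken the comparison the section does describe.
- **An observed reversal would prove little.** In the example it occurs 31% of the time with no growth factor at all.

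**Conclusion.** The point holds as a possible bias of limited scope in a descriptive primary safety summary. By default, only the MTD column mixes the two Cycle 1 support rules, with about 73% of its patients under the permissive one, and nothing planned would let a reader see how much support was given. Cycle 1 and worst-grade-on-study myelosuppression at the MTD may therefore be understated relative to other doses.

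Under an assumed 50% unsupported rate the shift runs from none, through about 7 percentage points (50% uptake, RR 0.6), to an upper bound of 11 to 25 points at full uptake with RR 0.7 to 0.3. By-visit tables from Cycle 2 fall under one rule in both parts, although Cycle 1 neutropenia can change later doxorubicin doses under 10.2.3; that carry-over is not quantified here. The problem can be removed cheaply because the SAP is still to be approved.

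**What to change.** In 14.3.3 to 14.3.5, or in the SAP before the expansion cohort opens:

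1. Require Cycle 1 haematology, worst-grade-on-study haematology and haematological TEAEs at the MTD to be shown separately for escalation and expansion patients. A pooled column may stand beside them.
2. Base dose-group comparisons of Cycle 1 haematological toxicity on escalation patients only, for whom one support rule applies at every dose.
3. Tabulate growth-factor use (patients and cycles) by study part, dose group and cycle, from the concomitant-medication data already collected.

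A comparison of cycles with and without growth factor is best left out, or labelled descriptive only: support is given in response to low counts, so supported cycles can look worse for that reason alone.

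The cost is SAP wording and a few more tables with smaller cells. No treatment rule and no data collection changes.
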